Step 1: In ANC: Healthcare providers provide counseling on HIV prevention and treatment at each ANC visit including HIV testing, as part of standard of care. In post-natal care and well-baby visits women may not receive regular HIV testing and messages and will receive this within step 2 (with study counselor). Following their ANC visit, enrolled women will be invited to attend the study site in each MOU to do the follow-up visit including the ACASI survey and prescription and adherence counseling (if on PrEP).

Step 2: ACASI survey at each visit in a private study room

Step 3: In the study room, the study counselors will provide PrEP-specific counseling including adherence counseling for those on PrEP (and management of side effects), or counseling about the risks and benefits of PrEP for women not yet on PrEP. Women not on PrEP will be asked if they are interested in starting PrEP at this visit.

Step 4: STI testing: At 3rd trimester visit and first postpartum visit, participants self-collect a vaginal swab for STI testing (chlamydia, gonorrhea and trichomonas vaginalis using Cepheid® point of care testing). Participants will be treated if diagnosed with a STI according to National Guidelines. They will receive a partner notification letter to bring their partner in for treatment as well.

Step 5 (for women on PrEP): At each visit the study counselor will ask, and record responses, all participants on PrEP about any side effects associated with TDF/FTC, including diarrhea, nausea, fatigue, headache and rash (which are seen in about 10% of participants during the initiation of therapy). We will encourage participants to contact the study nurse if they experience side effects between visits.

For participants on PrEP, the study nurse performs a blood draw for creatinine clearance and a finger prick for DBS testing for adherence measures and (if applicable for this visit). See Table 1 for study calendar.

Step 6: PrEP provision (for 1 or 2 months) and appointment reminder

Follow-up & retention: Tracing information will be taken at the enrolment visit and updated at each study visit. Retention activities will focus on scheduled measurement visits. Following our established approach in this setting, we will provide reminder calls to participants before their measurement visits, and initiate tracing, including home visits, for women who do not attend the measurement visit within one week of the scheduled visit.

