- **DBS:** Dried blood spots will be prepared from finger pricks every two months in women on PrEP to evaluate adherence.
 - DBS cards will be prepared and stored following standard protocols and stored at -80°C for analysis at the end of the study with the clinical pharmacodynamic laboratory of [name] at UCT. Using techniques developed by [name] at University of Colorado [16] adherence will be defined as red blood cells containing TDF-DP ≥ 40 ng/dl which is indicative of daily dosing [16]. As supplementary measures of PrEP adherence, we will use self-reported items that we will adapt from previous studies (including visual analogue scales as well as 3-day, 30-day and last visit recall questionnaires) (22-25), and pharmacy refill records to compare objective versus subjective measures and report on the effectiveness of each measure in correlation to the true measures of TDF-DP. We will determine final dosing and measures following reporting from ongoing PK studies of pregnant women on PrEP (e.g. Impaact 2009).

Laboratory tests in all women in the cohort:

- **STI testing (baseline, 3rd trimester and first postpartum visit):** Self-collected vaginal swab kits will be provided to all participants along with an explanation for their use. Swabs will be analyzed using on-site testing equipment (GeneXpert; Cepheid ®) for rapid testing of chlamydia, gonorrhoea and trichomonas vaginalis. If they test positive, they will be treated by the nurse/midwife in ANC or postpartum care and a referral for her partner to receive STI treatment in the clinic.
- **HIV testing.** As part of the standard of care, all pregnant and breastfeeding women will be tested for HIV using serial rapid HIV tests at each antenatal and postnatal care visit. In addition, PrEP-PP study staff will have a stock of rapid HIV test kits to ensure that women get tested at each study visit.
 - **Seroconversion.** If a woman, infant or partner seroconverts at any point during the study, they will be referred to the clinician on duty to initiate ART, following counseling about PMTCT, breastfeeding, disclosure, and ART adherence, per the SA National Protocols [17]. Seroconverted women will be censored from the remainder of the study and referred to the clinic to initiate ART.

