DBS taken for TDF-DP adherence measures (bi-monthly in participants on PrEP)	X	X	X		X		X		X		X		X		X			X
In-depth interviews for 20 participants							X											X
Collect study data on: (1) PrEP counseling, (2) PrEP medication when requested, (3) regular appointments, (4) IEC materials, (5) adherence counselling and support by facility, through patient ACASI survey at every study visit	X	X	X	X	X	X	X	X	X	X	X	X	X	X	X	X	X	X

Training, quality assurance and supervision:

1. *Existing DOH staff:* We will conduct an on-site half day training for existing counselors, nurses and midwives and Managers in the two study sites on the study protocol to ensure that they understand and support the integration of the study in their facility.

- a. **Inclusion of interviews for healthcare providers in health facility to understand their knowledge of and attitudes around PrEP:** We seek to interview existing health care providers including nurses, counselors, midwives and managers to understand their knowledge about PrEP, HIV prevention in pregnancy and any attitudes about PrEP that may affect future integration of

PrEP and PrEP uptake in the facility. We will interview approximately 20 health care providers and have one focus group in those providers in isiXhosa or Afrikaans. We will record, translate and transcribe their responses and analyze the results thematically in order to develop interventions around provider training and support.

2. *Study staff:* We will hire 2 counselors, 2 nurses, 2 coordinators who will receive a 3-day training program and they will be required to complete the entire training course. After completion of the training, the study PI will observe the counselor and nurse completing each step of the intervention with a mock patient. Upon satisfactory completion of observed sessions, the counselors and nurses will be certified to conduct the study intervention and will receive a completion certificate.
3. *Quality assurance* will occur on three levels. Day-to-day monitoring, supervision, and support of counselors will be carried out by the Study Coordinators (from UCT—1 per facility). The Study Coordinator will provide on the job training to ensure that counselors and nurses respect the study protocol. Adherence to the counseling protocol will be established by the Study Coordinator who will sit in on a random subsample of 20% of counseling sessions to ensure that counselors are adhering to study protocols.

Sources of data

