The primary analysis will focus on measuring the distribution of women across the PrEP cascade including: initiation, retention and adherence. **PrEP initiation** will be based on a woman’s uptake of PrEP and allow for stoppage and re-initiation; **PrEP retention** will be defined as not missing >1 visit among those on PrEP (with separate analyses of PrEP stoppage). For **PrEP adherence** for women on PrEP we will measure both **perfect adherence** (i.e. level of objective adherence throughout pregnancy and breastfeeding periods) as well as “**prevention-effective**” adherence (i.e. adherence before and during times of sexual activity) in participants through objective and subjective measures to evaluate agreement between the two measures, and the level of under- or over-reporting. Primary adherence analyses will use objective measures (TDF-DP from DBS) taken on all those who enrolled and initiated PrEP; subsidiary analyses will consider (i) other adherence measures and (ii) multiple imputation for missing adherence data.

- **Use of PrEP will be measured** through alternate definitions of the main outcomes (e.g. adherence by self-report versus adherence by pharmacy refill), compared using measures of agreement and will be analyzed as independent models to contrast estimated associations.

- **Measurement of prevention-effective execution:** Execution refers to PrEP adherence during a time when at-risk sex happens. It is calculated by: number of doses reported, or recorded/number of expected doses based on HIV risk and PrEP initiation/discontinuation
- **Prevention-effective continuation:** Prevention-effective continuation describes the duration of PrEP use during periods of HIV risk and references the absolute time of use during pregnancy and breastfeeding periods. We will adapt the methodology from previous PrEP studies in SA including FEM-PrEP to create a semi-ordinal composite adherence score from blood specimens from DBS every 2-months.

Table 2: Study measures for PrEP-PP

Primary Outcomes	Measurement	Source	Frequency
PrEP initiation	# of women who initiate PrEP over time / total # of women in active cohort = proportion of women who initiate PrEP	Electronic provider log (REDCap)	Daily entry, weekly analysis

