PrEP retention	# of women on PrEP who return for study visits (do not miss more than 1 visit) / total # of women in active cohort who are prescribed PrEP= proportion of women on PrEP who are retained in PrEP study	Electronic provider log (REDCap)	Daily, analysis weekly
PrEP adherence-subjective	# of women taking PrEP, who self-report taking their medication daily (& pill count to confirm this) during periods of sexual risk over time / total woman-time on PrEP in active cohort = PrEP adherence rate (subjective)	Electronic provider log (REDCap)	Daily, analysis weekly
PrEP adherence-objective	# of women taking PrEP who have >80% levels at >40ng/mL TDF-DP (indicating dosing in past 24 hours) at 3 rd trimester, delivery, and 6 weeks postpartum (and during sexual risk periods during that time) / total woman-time on PrEP in active cohort = PrEP adherence rate (objective)	Lab analysis of TDF-DP measures	Quarterly
Secondary Outcomes			
Predictors of attrition at key steps in the PrEP cascade	Individual, pill/study and disease specific predictors of attrition	ACASI	ACASI: Every study visit
HIV outcomes	HIV testing data: HIV-uninfected, HIV-positive for mother and child (if mother seroconverts)	Electronic provider log (REDCap)	Every visit
Health outcomes and adverse events	Any side-effects, creatinine, any negative maternal or neonatal outcomes (for mother and infant)	Electronic provider log (REDCap)	During routine lab tests and visits

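### The three-point objective-adherence outcome in Table 2 cannot be scored from the Table 1 blood-spot calendar, and it stops at 6 weeks postpartum

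*Combined protocol and SAP*

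**What the plan says.** Section 6 (Statistical analysis considerations) makes DBS drug levels the primary adherence measure, for all women who enrol and initiate PrEP. It describes perfect adherence as the "level of objective adherence throughout pregnancy and breastfeeding periods". Table 2 in the same section turns this into a listed primary outcome: levels above a threshold at the third trimester, "delivery, and 6 weeks postpartum (and during sexual risk periods during that time", with the frequency given as quarterly.

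The sampling itself is set in Section 5:

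- The laboratory text says "Dried blood spots will be prepared from finger pricks every two months in women on PrEP to evaluate adherence". It adds that the cards are "stored at -80°C for analysis at the end of the study".
- The follow-up steps call for "a finger prick for DBS testing for adherence measures and (if applicable for this visit). See Table 1 for study calendar", so Table 1 governs.
- The Table 1 row reads "DBS taken for TDF-DP adherence measures (bi-monthly in participants on PrEP" and carries marks at months 1, 2, 3, 5, 7, 9, 11, 13, 15 and 18.
- Follow-up visits are monthly to birth and two-monthly afterwards. The text names no delivery visit and no 6-week visit.

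Section 6 also plans a "semi-ordinal composite adherence score from blood specimens from DBS every 2-months" and models adherence over the study with mixed-effects probit models and generalized estimating equations.

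**The concern.** A listed primary outcome should be computable from the samples the plan collects. Here the outcome names three time points, and the calendar appears to supply samples for two. Whoever scores it must choose a rule that the plan does not give: leave delivery out, call it a failure, or use one sample twice. Because the cards are assayed at the end of the study, that choice could be made with the rest of the data in view.

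The second worry is coverage. The study exists to estimate the PrEP cascade through 12 months postpartum, yet the headline objective figure would describe only the weeks around birth. Women not on PrEP are asked again at each visit whether they want to start. A woman who first starts after 6 weeks postpartum is in the primary adherence population but has no Table 2 time point at all.

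**Working it through.** The plan gives no figure to reproduce on this point. The check sets Table 2 against Table 1.

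**Anchoring the months.** The Table 1 header puts months 1 to 6 in pregnancy and 7 to 18 postpartum, so nominal delivery is the boundary between months 6 and 7. The STI row is marked at months 1, 5 and 7, and the text places STI tests at baseline, third trimester and first postpartum visit. Hence third trimester = month 5 and first postpartum visit = month 7.

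**Weeks postpartum.** One month = 365.25 / 12 / 7 = 4.35 weeks.

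- If columns are intervals: month 7 covers 0 to 4.3 weeks, month 8 covers 4.3 to 8.7, month 9 covers 8.7 to 13.0. Six weeks falls in month 8.
- If month 18 means 12 months postpartum exactly, month 7 is 1 month = 4.35 weeks, which is 6 − 4.35 ≈ 1.7 weeks short of 6 weeks.

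| Table 2 point | Nominal place in Table 1 | DBS there? |
|---|---|---|
| Third trimester | month 5 | yes |
| Delivery | boundary of months 6 and 7 | month 6: visit but no DBS; month 7: DBS |
| 6 weeks postpartum | month 8, or between months 7 and 8 | month 8: no DBS; nearest is month 7 |

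Month 8 has no mark in the counselling, routine-care or ACASI rows either. Only the general data-collection row, which is ticked in every month, includes it. On either reading, month 7 is the one sample near both delivery and 6 weeks; the next is month 9.

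**Effect on scoring.** Suppose the 80% criterion in Table 2 is read as the share of time points above threshold, an assumption because the wording is unclear. With three points the possible shares are 0, 33, 67 and 100%, so a woman must pass all three. With one point unsampled:

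- missing counted as failure: the best possible is 2/3 = 67%, and no woman can be classed as adherent;
- missing dropped: 2/2 = 100% is attainable;
- month 7 used for both points: 3/3 is attainable, with one sample counted twice.

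**Coverage.** Table 1 has six postpartum DBS months (7, 9, 11, 13, 15, 18). Five (9 to 18) fall after the Table 2 window. Twelve months is 12 × 4.35 = 52.2 weeks, so 6 weeks is 6 / 52.2 ≈ 11% of postpartum follow-up.

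**Frequency.** The gaps between the ten Table 1 samples are 1, 1, 2, 2, 2, 2, 2, 2 and 3 months. Strict two-monthly sampling from month 1 gives nine samples (1, 3, …, 17). Strict quarterly sampling gives six (1, 4, …, 16 or 3, 6, …, 18). The grid matches neither.

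**Month 1.** This is the enrolment visit, where the first supply is handed out. For a woman starting that day, a DBS precedes or coincides with her first dose and carries no adherence information. The enrolment steps list creatinine and hepatitis B blood tests but no DBS, and nothing says whether the month-1 mark is a baseline.

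**The case against.** Several points on the other side are sound.

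- Month 7 is a DBS month, and the plan does not fix its week. It could serve delivery or 6 weeks. A reader might infer that neither point has a sample; the calendar does not support that. What stands is that one sample cannot supply both.
- Table 1 is nominal. Gestation at enrolment varies, so some women will have a DBS closer to delivery than the grid suggests. That helps individuals by chance but gives no rule for scoring.
- A reader might infer that the samples after 6 weeks go unused. They do not: Section 6 feeds two-monthly DBS into the composite score and models adherence across the study. Only the Table 2 summary stops early.
- A reader might infer that the month-1 sample pushes adherent women under the 80% cut-off. Under the three points of Table 2, month 1 never enters the score. The mark may be a baseline; the gap is only that the plan does not say so.
- Quarterly may describe laboratory runs, since that column of Table 2 mixes data entry and analysis. That reading conflicts with assay at study end. The label in Table 1 and the text agree with each other, and the grid follows the PrEP-refill row exactly, so its pattern has a logic.
- The study is a pilot, not powered for comparisons between cascade steps, and the plan says final measures await pharmacokinetic results. This excuses imprecision and an unsettled threshold. It does not settle when samples are scored.
- Redefining the outcome on Table 1 visits replaces a peripartum outcome the sponsor may have wanted. This is a fair cost, stated under the fix.

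**Conclusion.** The point holds as an inconsistency in a listed primary outcome. On the nominal calendar, Table 1 supplies separate samples for at most two of the three Table 2 time points, and no delivery sample is planned, so the three-point outcome cannot be scored as written. The summary covers about the first 11% of postpartum follow-up, although Section 6 describes adherence throughout pregnancy and breastfeeding; the five later DBS visits inform only the composite score and the models. Three sampling patterns can be read from the plan and need reconciling.

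This rests on Table 1 being the governing calendar, as the follow-up steps state, and on month 5 and month 7 being the third-trimester and first postpartum visits, as the STI schedule implies. The 67% versus 100% contrast rests further on reading the 80% criterion as a share of time points. The documents do not support a claim that later data are wasted or that women are misclassified by the month-1 sample.

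**What to change.** Rewrite the Table 2 row so that objective adherence is defined on named Table 1 DBS visits after PrEP start: for example month 5 for the third trimester, month 7 for the first postpartum visit, then the later postpartum visits. Because Table 1 is nominal, say how a visit is assigned when delivery falls in a different study month. Report the proportion above threshold by visit and by period (pregnancy, early postpartum, to 12 months postpartum), and state how a missed DBS is handled.

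State that a DBS taken on the day PrEP is first dispensed, which is month 1 for women starting at enrolment, is a baseline and is not scored. Use one description of sampling frequency in Table 2, the laboratory text, the composite-score text and the Table 1 label, matching the grid. If quarterly refers to assay batches, say so and reconcile it with assay at study end.

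The cost is wording in Section 6 and the two tables; the samples are already planned. The downside is that the separate delivery time point is dropped or merged with the first postpartum visit. Keeping it would need an added sample. The change should be made before the stored cards are assayed, so that the definition is not chosen after the results are known.

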Our team is comprised of highly experienced adolescent HIV prevention researchers, including [name] and [name], who have a long history of research that seeks to address the key health issues facing South African adolescent girls while at the same time protecting this vulnerable population. The research sites have considerable experience in conducting clinical research in adolescent populations.

Figure 2. HIV incidence (%) by age and sex in South Africa

[figure not shown]
[figure not shown]

Figure 3. Adolescent pregnancy in South Africa, 2010-2013

Our study, PrEP-PP (PrEP in Pregnant and Postpartum women) will determine the distribution of women across the PrEP cascade (i.e. PrEP initiation, retention, and adherence) in a cohort of HIV- pregnant and breastfeeding adolescent girls and women in two public health facilities in South Africa to inform policymakers about the efficacy of PrEP integration into antenatal (ANC) and postnatal care in high HIV incidence communities.

2. Study objectives:

The objectives of the study are to:

1. Determine the distribution of women across the PrEP cascade:
 - (1) Evaluate the proportion of pregnant and breastfeeding women who initiate PrEP out of all women offered PrEP
 - (2) Evaluate the proportion of pregnant and breastfeeding women who are retained in the PrEP cohort
 - (3) Evaluate the proportion of pregnant and breastfeeding women who initiate PrEP who adhere to PrEP using objective dried blood spot measures and subjective measures of self-reported pill count and adherence
 - (4) Evaluate the proportion of pregnant and breastfeeding women on PrEP (and not on PrEP) who acquire HIV, who transmit HIV to their infant, and who report adverse events
2. Evaluate patient and provider-level factors associated with the PrEP cascade using quantitative and qualitative approaches (including in-depth interviews)

3. Study design

To address these objectives, we will conduct an observational cohort study in 220 pregnant women who will be recruited at the first antenatal care (ANC) visit from the Gugulethu Midwife Obstetric Units in Cape Town. We will follow the enrolled women through 12-months post-delivery.

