Each outcome will be described via cumulative incidences at fixed intervals (e.g., cumulative PrEP initiation by delivery) and incidence densities over time. The general statistical approaches to these outcomes are analogous; data will be described graphically, including product-limit graphs, with preliminary analyses based on standard approaches for rates and proportions. The modelling approach will vary depending on the nature of the outcome. **PrEP initiation** will be modelled using a probit model (preferred to estimate risk factors for common outcomes) with individual-level covariates as fixed effects; when time-dependent or visit-specific covariates are included in the analysis of cumulative initiation we will shift to a mixed-effects setting with random effects around individual participants. **PrEP retention** will be examined using similar approaches; in addition, we will use time-to-event methods to estimate factors associated with time to loss (non-retention) among women having initiated PrEP. **PrEP adherence** will be modelled using mixed effects probit models as above and generalized estimating equations to examine the marginal effect of individual-level covariates on adherence during the study [85]. Throughout, robust estimates of standard errors will be used.

The same modelling approaches will be used to explore secondary implementation questions such as the effect of individual, pill/study, and disease factors on PrEP initiation, retention and adherence outcomes (see Figure 1 for conceptual model). The main exposures include: **individual level factors**: risk perception, community/family support, sexual activity, risk, concerns about drug's side effects and harm on self (pregnancy) and/or infant's health. **Pill regimen and study factors** include: PrEP side effects, time required to participate in study, patient-provider relationship measured from the participants' perspective. **Disease factors** include: stigma around HIV and PrEP, and partner's HIV status (see Table 5 for specific variables).

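### Both adherence rows of Table 2 divide a count of women by woman-time on PrEP, so neither gives the proportion of initiators that Objective 1(3) asks for

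*Combined protocol and SAP*

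**What the plan says.** Section 2 (Study objectives), Objective 1(3): "Evaluate the proportion of pregnant and breastfeeding women who initiate PrEP who adhere to PrEP using objective dried blood spot measures", with self-reported measures named alongside. This is a proportion with initiators as the denominator.

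Section 6, Table 2 lists four primary outcome rows:
- Initiation: women who initiate over "total # of women in active cohort = proportion of women who initiate PrEP".
- Retention: women on PrEP who keep attending over "total # of women in active cohort who are prescribed PrEP= proportion of women on PrEP who are retained in PrEP study".
- Adherence, subjective: a number of women over "total woman-time on PrEP in active cohort = PrEP adherence rate (subjective").
- Adherence, objective: a number of women over "total woman-time on PrEP in active cohort = PrEP adherence rate (objective").

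The first two rows are women over women and are labelled proportions. The last two are women over time and are labelled rates. Both adherence numerators also carry a condition about periods of sexual risk. The objective row names three time points: third trimester, delivery and 6 weeks postpartum. The subjective row names none.

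The text of section 6 (Statistical analysis considerations) adds three relevant statements. On the analysis set: "Primary adherence analyses will use objective measures (TDF-DP from DBS) taken on all those who enrolled and initiated PrEP". On description: "Each outcome will be described via cumulative incidences at fixed intervals (e.g., cumulative PrEP initiation by delivery) and incidence densities over time". On dose-level execution: "number of doses reported, or recorded/number of expected doses based on HIV risk and PrEP initiation/discontinuation". Adherence is modelled with mixed-effects probit models and generalized estimating equations (GEE).

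**The concern.** A count of women divided by woman-time is not a proportion. It has no upper limit of 1. Its value changes with how long women stay on PrEP or, if women are counted repeatedly, with how often they are seen. Adherence at set visits is a status a woman can hold, lose and regain. It is not an event with an incidence, so an incidence-type rate is not a natural summary of it.

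Section 6 describes the study as a pilot whose product is estimates of the PrEP cascade, and adherence is one of the cascade's primary steps. If the two rows are computed as written, the reported figure will not say what share of initiators adhered. Nor can it be placed beside the initiation and retention proportions.

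**Working it through.** The plan states no expected adherence, time on PrEP or precision, so there is no figure of its own to reproduce. The check is one of units, followed by illustrations. Numbers of women, adherence levels and times on PrEP are assumptions; visit months come from Table 1.

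**Units.** Women ÷ woman-months = 1/month. Objective 1(3) needs women ÷ women, which has no units.

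**Objective row, each woman counted once.** Assume 100 initiators of whom 60 adhere, a proportion of 60%. The Table 2 figure is 60 ÷ (100 × mean months on PrEP):

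| Mean months on PrEP | Woman-months | Per woman-month | Per woman-year |
|---|---|---|---|
| 3 | 300 | 0.200 | 2.40 |
| 6 | 600 | 0.100 | 1.20 |
| 12 | 1200 | 0.050 | 0.60 |
| 18 | 1800 | 0.033 | 0.40 |

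The proportion is 60% in every line.

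**Objective row, women counted at each of the three time points.** With 60 of 100 adherent at each, the numerator is 180. At 6 months' mean use, 180/600 = 0.30 per woman-month (3.60 per woman-year). At 12 months, 180/1200 = 0.15 (1.80 per woman-year). The level changes but the units are still 1/time.

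**Bounding woman-time at 6 weeks postpartum (1.38 months), each woman counted once.** If PrEP starts 6 months before delivery, 0.60/(6 + 1.38) = 0.081 per woman-month. If it starts 2 months before, 0.60/(2 + 1.38) = 0.178. The ratio is 7.38/3.38 = 2.18 for the same 60%. A window alone does not cure the problem.

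**Early stopping, each woman counted once.** Suppose the 60 adherent women stay 18 months and the other 40 stop at 1 month. Woman-months are 60 × 18 + 40 × 1 = 1120, and 60/1120 × 12 = 0.643 per woman-year. If all 100 stay 18 months the figure is 0.40. The proportion is 60% both times.

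**Subjective row, read as repeated counts over visits.** Table 1 shows follow-up visits in pregnancy at months 2 to 6 (5 visits) and postpartum visits at months 7, 9, 11, 13, 15 and 18 (6 visits in 12 months). A woman adherent at every visit scores 5/5 = 1.00 per month in pregnancy (5/6 = 0.83 if month 1 is included in the time) and 6/12 = 0.50 per month postpartum. Her adherence has not changed; only the visit spacing has.

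**The cut-off in the objective numerator.** The DBS paragraph in section 5 gives the TDF-DP threshold as 40 in ng/dl; Table 2 gives 40 in ng/mL. Since 40 ng/mL = 4000 ng/dl, the two differ 100-fold.

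**The case against.** The best defence is that the rest of section 6 points to a proportion. It promises standard methods for both rates and proportions, and cumulative incidences as well as incidence densities. It takes all women who enrolled and initiated PrEP as the adherence set, and it fits probit models, which need a binary outcome. On that view the Table 2 rates are loosely worded person-time companions. This stands in part: the text is compatible with the right proportion. But it never restates the two rows, and the general sentence on incidence densities covers every outcome without giving adherence a count-based denominator.

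A second defence is that the subjective numerator, which speaks of adherence over time, means adherent woman-time, so that the ratio has no units. The row says a number of women. Even on the kinder reading, the answer is a share of time on PrEP, not of initiators.

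A third is that little depends on the ratio: no group comparison on it is planned, and the correct proportion can be computed from data already planned. This is fair, and it limits the weight of the point.

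Two stronger readings should be resisted. A reader might infer that the objective row counts each woman once, so that its figure must fall as time on PrEP lengthens. The row does not say whether its 80% rule applies per woman or per time point, so single counting is only one reading. A reader might also infer that women who stopped PrEP must count as not adherent. Section 6 defines adherence for women on PrEP, analyses stoppage separately, and ties expected doses to risk and discontinuation. Section 5 also provides for study-directed stops after renal results. The documents do not settle the matter that way.

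**Conclusion.** The two rows are wrong as written. Followed literally, they give a quantity in units of 1/time that does not answer Objective 1(3), under every reading that keeps a count of women in the numerator. In the illustration, 60% adherence appears as anything from 2.40 to 0.40 per woman-year as mean use goes from 3 to 18 months. Those values rest on assumed adherence and duration and on single counting. The mismatch of units rests on the text alone.

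The fault lies in the definition of a descriptive primary outcome. A reader might infer that the planned adherence analyses as a whole are invalid; the documents do not support that. The probit and GEE models and the agreement analyses do not use the ratio, and the dose-level execution measure is defined separately. The correction should still be made before analysis, because cascade estimates are what this pilot is meant to deliver.

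**What to change.** 1. Restate both rows as adherent women ÷ women who had initiated PrEP by each named time point, keeping the sexual-risk-period condition as it stands. Name the time points for the subjective row too.
2. Report alongside this the proportion among women on PrEP with a measurement at that time point.
3. Show women who stopped PrEP, including study-directed stops, as a separate category, so that persistence and adherence can be told apart.
4. If a time-based measure is also wanted, define it as adherent woman-time ÷ total woman-time on PrEP over the same stated window.
5. State whether the 80% rule applies per woman or per time point. Across three samples, a woman-level rule above 80% requires all three, since 2/3 = 67%.
6. Reconcile the TDF-DP cut-off units between the DBS paragraph of section 5 and Table 2. Section 5 treats the final measures as provisional, pending pharmacokinetic studies in pregnancy, so the reconciliation can be made when they are fixed.

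The cost is rewording two table rows and the matching analysis code. The sampling scheme does not change.
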